
- Olanzapine + Samidorphan (5 mg)
- Olanzapine + Samidorphan (10 mg)
- Olanzapine + Samidorphan (20 mg)
- Olanzapine + Placebo

All study drug will be taken once daily by mouth. Olanzapine and samidorphan/placebo tablets should be taken together (ie, at the same time). Randomization will be stratified by the amount of weight change during the olanzapine lead-in period (ie, from Day 1 to Day 8), with subjects grouped into the following 3 strata:

- Weight change ≤ 0 kg
- Weight increase >0 to <1 kg
- Weight increase ≥ 1 kg

Subjects will be discharged from the inpatient unit on Study Day 10 (Visit 5) and will return on Study Day 15 (Visit 6).

Subjects are not required to be taking any antipsychotic medication at the time of screening or Visit 2. However, those who are will be tapered off of their prior antipsychotic medication within two weeks after initiation (ie, by Study Day 15, Visit 6). This cross-taper from prior antipsychotic treatment to olanzapine will be conducted under the care and discretion of the PI and consistent with current clinical practice.

After Study Day 15 subjects will return to the clinic weekly through the first month of double-blind treatment (ie, Study Day 36) and then every 2 weeks thereafter for the remainder of Part A. Any subject who prematurely discontinues during Part A will be asked to return to the clinic for an early termination (ET) visit and will be asked to return for follow-up visits 2 and 4 weeks later.

Part A Visit Schedule

	Screening	Olanzapine Lead-In	Double-Blind Placebo-Controlled Treatment Period										Transition*
Visit	1	2	3	4	5	6	7	8	9	10	11	12	13
Day	-30 to -1	1	8	9	10	15	22	29	36	50	64	78	92
Week			1			2	3	4	5	7	9	11	13

* Transition (Visit 13) is the end of Part A and the beginning of Part B (Part B begins with dosing at Visit 13). Shaded cells represent inpatient stays.

Assessments prior to study drug administration at Visit 13 (the transition visit) will serve as end of Part A assessments; dosing and post-dose assessments will be considered Part B assessments.

Part B (Active ALKS 3831 Treatment and Safety Follow-up Periods)

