After completion of Part A (ie, at Visit 13), subjects will transition into Part B and will continue onto a 12-week active treatment period during which all subjects will receive ALKS 3831 (ie, olanzapine plus samidorphan). Subjects who had been receiving ALKS 3831 during the double-blind period will continue on the same dose for the 12-week active treatment period. Subjects who had been receiving olanzapine + placebo in the double-blind period will continue on the same dose of olanzapine and will be transitioned from placebo to samidorphan (at the highest dose).

At Visit 13 (Study Day 92), subjects will be admitted for a 2-night inpatient stay (Visits 13-15, Study Days 92-94) to allow for monitoring following initiation of samidorphan dose in subjects originally assigned to the olanzapine + placebo group. The inpatient stay is required for all subjects. After discharge (Study Day 94), subjects will return 5 days later for Visit 16 (Study Day 99). After Visit 16, subjects will be seen weekly for the next 3 weeks (Visits 17-19) and then at 2-week intervals for the remainder of the study (Visits 20-25).

The subject will take the final samidorphan dose the night before Visit 23 (Study Day 176). No samidorphan dose will be administered onsite during Visit 23. Olanzapine dosing will continue uninterrupted through a 4-week follow-up period: A safety follow-up visit will occur 2 weeks after and

4 weeks after Visit 23. Any subject who prematurely discontinues from the study during Part A or Part B will be asked to return to the clinic for an ET visit and follow-up visits 2 and 4 weeks after the ET visit.

Part B Visit Schedule

	Transition*	Active ALKS 3831 Treatment Period										Follow-Up	
Visit	13	14	15	16	17	18	19	20	21	22	23/ET	24	25
Day	92	93	94	99	106	113	120	134	148	162	176	190	204
Week	13			14	15	16	17	19	21	23	25	27	29

* Transition (Visit 13) is the end of Part A and the beginning of Part B (Part B begins with dosing at Visit 13)
Shaded cells represent inpatient stays.

Number of subjects (planned): Approximately 280 subjects will be randomized.

Diagnosis and main criteria for inclusion:

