5.2.1. Samidorphan

Samidorphan is a new chemical entity in clinical development by Alkermes. It is an opioid modulator which acts primarily as an antagonist at μ opioid receptors, with mixed agonist/antagonist activity at δ and κ receptors. It is currently being investigated as a single agent for the treatment of reward disorders, in combination with buprenorphine for the treatment of major depressive disorder and for the treatment of cocaine dependence, and in combination with olanzapine for the treatment of schizophrenia. Based on its chemical structure, samidorphan is a Schedule II controlled substance according to the US Drug Enforcement Agency and will require proper handling (see [Section 10](#)).

Ten clinical studies of samidorphan have been conducted to date, 8 of which included subjects that received samidorphan alone (not in combination with another product). Overall, approximately 600 subjects have been exposed to samidorphan. Commonly reported adverse events (AEs) observed across all studies included nausea, fatigue, and somnolence. Overall, no trends or clinically meaningful changes have been observed in clinical laboratory analytes, vital sign parameters, or electrocardiogram (ECG) data.

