All study drug will be taken once daily, by mouth, at the same time. Subjects will be encouraged to take study drug in the evening or at bedtime. Study drug administration may be adjusted to accommodate study procedures. Randomization will be stratified by the amount of weight change during the olanzapine lead-in period (ie, from Day 1 to Day 8), with subjects grouped into the following 3 strata:

- Weight change ≤ 0 kg
- Weight increase >0 to <1 kg
- Weight increase ≥ 1 kg

This stratification will be used for analyses of secondary endpoints as specified in the statistical analysis plan (SAP).

Subjects will be discharged from the clinic on Study Day 10 (Visit 5), and will return on Study Day 15 (Visit 6).

Subjects are not required to be taking any antipsychotic medication at the time of screening or Visit 2. However, those who are will be tapered off of their prior antipsychotic medication within 2 weeks after initiation (ie, by Study Day 15, Visit 6). This cross-taper from prior antipsychotic

treatment to olanzapine will be conducted under the care and discretion of the PI and consistent with current clinical practice.

After Study Day 15 subjects will return to the clinic weekly through the first month of double-blind treatment (ie, Study Day 36) and then every 2 weeks thereafter for the remainder of Part A. Any subject who prematurely discontinues during Part A will be asked to return to the clinic immediately for an ET visit and after 2 and 4 weeks for follow-up visits.

Assessments prior to study-drug administration at Visit 13 (the transition visit) will serve as end of Part A assessments; dosing and post-dose assessments will be considered Part B assessments.

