Pharmacogenetic blood sample			X										
Blood samples for PK		X	X	X	X	X	X	X	X	X	X	X	X
Personal and Social Performance Scale (PSP)		X	X							X			X
Food Craving Inventory (FCI)		X	X			X							X
Impact of Weight on Quality of Life – Lite Questionnaire (IWQOL-Lite)		X	X										X
Interactive Web Response System (IWRS)			X	X	X	X	X	X	X	X	X	X	X
Olanzapine Dosing		X	X	X	X	X	X	X	X	X	X	X	X
Double-Blind Samidorphan/ Placebo Dosing ¹⁴			X	X	X	X	X	X	X	X	X	X	
Adverse Event (AE) Monitoring	X	X	X	X	X	X	X	X	X	X	X	X	X

	Screening	Olanzapine	Double-Blind Placebo-Controlled Treatment Period										Transition ¹
	Outpatient Visits		Inpatient Stay			Outpatient Visits						Inpatient Stay ²	
Study Visit	1	2	3	4	5	6	7	8	9	10	11	12	13
Study Day	-30 to -1	1	8 (±1)	9 (±1)	10 (±1)	15 (±1)	22 (±2)	29 (±2)	36 (±2)	50 (±2)	64 (±2)	78 (±2)	92 (±2)
Study Week			1			2	3	4	5	7	9	11	13
Concomitant Medication Review	X	X	X	X	X	X	X	X	X	X	X	X	X
Clinical Validation Inventory for Study Admission (C-VISA TM)	X												

¹ Transition Visit = the end of Part A and the beginning of Part B. Assessments at this visit are included in both schedules for convenience.

² All measures should be taken pre-dose at Visit 13 except where indicated

³ Height will be measured at screening only; weight and waist circumference will be measured at all indicated visits

⁴ Serum pregnancy test at screening; urine pregnancy test at other time points

⁵ Centralized drug screen testing at screening, local drug screen testing via dipstick at other time points. The urine drug screen includes benzodiazepines, opioids, amphetamine/methamphetamine, and cocaine.

⁶ Alcohol use only

⁷ Orthostatic blood pressure and heart rate measurements will be taken anytime pre-dose and approximately 1 hour post-dose at Visits 3 - 6 and Visit 13 only. At all other dosing visits, routine vital sign assessments will be conducted anytime pre-dose. At all other visits (when no dosing occurs) assessments will be conducted anytime.

⁸ Collect pre-dose and post-dose data

⁹ An overnight fast is required for labs at Visit 2, Visit 3, and Visit 13. Thyroid stimulating hormone should be assessed at screening only.

¹⁰ ECG will be measured anytime pre-dose and approximately 3 hours post-dose except for Visit 1 and Visit 2 where only 1 ECG will be done. For Visit 2, the ECG should be completed before dosing. For Visit 6, dosing may be done earlier than normal to accommodate post-dose procedure.

¹¹ Collect data pre-dose

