8.3.22. Drug Dispensation and Reconciliation

[Section 9](#) provides information related to drug dispensing procedures. The study drug use and storage information will be explained to/reviewed with the subject.

Study drugs include samidorphan and matching placebo tablets, and olanzapine tablets, all for oral administration. Samidorphan is a Schedule II substance, and should be stored, dispensed, and otherwise handled in accordance with the associated regulations.

Olanzapine will be prescribed by the PI and dispensed for oral administration by study staff.

During the inpatient stays, study drug will be dispensed once daily, and the time of administration will be at the discretion of study staff. Time of administration at any visit (inpatient or outpatient) may be adjusted as needed to accommodate post-dose measurements. Before being discharged from each inpatient stay, and at each post-randomization outpatient visit until Visit 23/ET, all subjects will receive blister cards containing samidorphan or placebo for self administration. Subjects will be instructed to take 2 tablets per day from the blister card in addition to their olanzapine tablet(s) once daily in the evening or at bedtime until Visit 23. The subject will take the final samidorphan dose the night before Visit 23. No samidorphan dose will be administered onsite during Visit 23. Olanzapine dosing will continue uninterrupted. Two safety follow-up visits will occur 2 and 4 weeks after Visit 23. Any subject who prematurely discontinues from the study during Part B will be asked to return to the clinic for an ET visit and follow-up visits 2 and 4 weeks after the ET visit.

Subjects will be instructed to keep all unused tablets in their blister card and not to mix tablets between blister cards and bottles.

Subjects will be instructed to return the original containers and any remaining study drug at each subsequent visit. Study drug accountability will be documented as the number of tablets

dispensed, dosed, lost/missing, or remaining. If applicable, the site will discuss noncompliance with the subject.

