3.1.1 Baseline Definition

Baseline for Part A is defined as the last non-missing observation on or before the first dose of study drug following randomization at Visit 3 (Day 8).

Baseline for Part B is defined as the last non-missing observation on or before the date of the first dose of study drug at Visit 13 (Day 92).

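### SAP 3.1.1 ties the Part B baseline to the date of the Visit 13 dose, so a same-day post-dose blood pressure, heart rate or ECG reading can become the baseline; this matters only if Part B vital-sign or ECG summaries use that baseline, which the SAP does not say

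*SAP*

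**What the plan says.** **Baselines.** SAP 3.1.1 gives two definitions. For Part A, with Visit 3 as the reference visit: "Baseline for Part A is defined as the last non-missing observation on or before the first dose of study drug following randomization". For Part B, with Visit 13 as the reference visit: "Baseline for Part B is defined as the last non-missing observation on or before the date of the first dose of study drug". The first refers to the dose and the second to its calendar date. The second has no pre-dose condition.

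**Visit 13 timing.** Orthostatic blood pressure and heart rate are "taken anytime pre-dose and approximately 1 hour post-dose at Visits 3 - 6 and Visit 13 only" (Protocol Table 1, vital-signs footnote). Protocol 8.3.6 and Table 2 repeat the pre-dose and 1-hour post-dose pair for Visits 13 to 16. Protocol 8.3.9 and Table 2 place an ECG before the dose and about 3 hours after it at Visits 13, 15 and 16. A Table 2 footnote requires all other Visit 13 data to be collected before dosing.

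**Which part the readings belong to.** In the Synopsis and again in 8.1.1, the protocol makes pre-dose Visit 13 assessments the end of Part A, while "dosing and post-dose assessments will be considered Part B assessments".

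**Where a baseline is used.** SAP 3.6.1.1 (PANSS) and 3.6.2.1 (weight) call explicitly for change from the Part B baseline. SAP 3.7.4 (vital signs) and 3.7.5 (ECG) speak only of baseline and post-baseline. SAP 3.7.1 extends the safety analyses to both parts.

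**The concern.** The last observation on or before a date includes anything recorded later that day. At Visit 13 the later reading follows the dose that the Part B baseline is meant to precede. An on-treatment value would then be the reference for on-treatment change, and the Visit 13 post-dose reading could not show any change.

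Visit 13 matters because former placebo subjects start samidorphan there. The protocol gives the purpose of the inpatient stay as "to allow for monitoring following initiation of samidorphan dose in subjects originally assigned to the olanzapine + placebo group". The post-dose readings at that visit are part of this monitoring. The placebo arm has 70 planned subjects, so at most 70 would have their first samidorphan exposure at Visit 13, and fewer after dropout in Part A.

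**Working it through.** The SAP gives no figure to reproduce on this point. The check is to apply the rule to the visit schedule.

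**1. Which variables have a post-dose reading at Visit 13.** Blood pressure and heart rate (about 1 hour) and ECG (about 3 hours) do. PANSS, CGI-S, weight, laboratory values and C-SSRS have none scheduled, so the date wording does not affect their Part B baseline.

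**2. Which reading the rule picks.** If the post-dose reading is non-missing and falls on the dosing date, it is the last observation on or before that date and displaces the pre-dose reading. If it is missing or falls after midnight, the pre-dose reading is picked. The cut-offs in dosing time are:

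- blood pressure and heart rate: 24:00 − 1 h = about 23:00
- ECG: 24:00 − 3 h = about 21:00

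Protocol 8.1.1 says "Subjects will be encouraged to take study drug in the evening or at bedtime", but for inpatient stays 8.3.22 says "the time of administration will be at the discretion of study staff". The share of subjects on each side of these cut-offs cannot be derived. Within one trial, some Part B baselines could be pre-dose and others post-dose, depending only on the clock.

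**3. Whether another SAP rule settles it.** SAP 3.11.1.1 keeps one valid value per scheduled visit without saying which, and refers repeat measurements to Section 3.1. Section 3.1 has a rule only for body weight (the median of three). Neither selects the pre-dose or the post-dose reading.

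**4. Which baseline 3.7.4 and 3.7.5 use.** They do not say. SAP 3.6.2.1 uses the unqualified word for change in both parts and then adds change from the Part B baseline separately. That usage suggests, without stating it, that the unqualified word in 3.7.4 and 3.7.5 means the Part A baseline.

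**5. Consequence under each reading.** Let d be the Visit 13 post-dose value minus the Visit 13 pre-dose value, and y a later value minus the Visit 13 pre-dose value.

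| | Part A baseline used | Part B baseline used, post-dose reading picked |
|---|---|---|
| Visit 13 post-dose change | unaffected | d − d = 0 |
| Later Part B change | unaffected | y − d instead of y |
| Post-dose vital-sign sets lost as post-baseline | none | 1 of 4 (Visits 13, 14, 15, 16) |
| Post-dose ECGs lost as post-baseline | none | 1 of 3 (Visits 13, 15, 16) |

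**6. Effect on the criteria, if the Part B baseline is used.**

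- *Table 5* is a joint criterion. Systolic low needs a value of 90 mm Hg or less and a fall of at least 20 mm Hg, that is, y − d ≤ −20. The absolute limit does not involve baseline, so d can alter status only for readings that already meet it. The other blood pressure and pulse criteria have the same form.
- *Table 6* has two change bands, 30 < change ≤ 60 ms and change > 60 ms. Replacing y by y − d can move a reading into, out of or between them.
- *Orthostatic criteria* compare standing with supine or use a standing rate. Only the post-baseline label of the Visit 13 reading is at stake.

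The documents give no value for d, and it can take either sign, so no shift in counts can be calculated.

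**The case against.** The strongest defence is that no analysis in the SAP is shown to be harmed. The Part B baseline is named only for PANSS and weight, both collected before the dose at Visit 13. For vital signs and ECG the SAP's usage leans to the Part A baseline, under which the wording does nothing. That stands, and it is why the point is minor.

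It can also be said that a sensible analyst would take the pre-dose value anyway. The protocol treats the post-dose reading as Part B data, SAP 3.10 declares no deviations, and a change row that is zero by construction would be pointless. If the single value kept under 3.11.1.1 were the pre-dose one, no post-dose value would remain to be picked. These are good reasons to think a pre-dose baseline was intended, but the SAP does not state it, and 3.1.1 read literally gives the opposite result. The protocol passages sort readings into parts without defining a baseline, so the mismatch is between a literal rule and that sorting, not between two baseline definitions.

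A reader might infer that the plan hides acute effects of first samidorphan exposure, or that Part B event counts are biased downward. The documents do not support either. The shift can go both ways, its size is unknown, and Protocol 5.2.1 reports that "no trends or clinically meaningful changes have been observed in clinical laboratory analytes, vital sign parameters, or electrocardiogram (ECG) data", so it may be close to zero. The readings also remain in the subject listings (SAP 3.1 and 3.7.4).

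**Conclusion.** The Part B baseline wording in SAP 3.1.1 is wrong as written: taken literally, it allows an on-treatment reading as baseline for blood pressure, heart rate and ECG. The effect depends on three conditions: that 3.7.4 or 3.7.5 uses the Part B baseline, that the post-dose value is the one taken, and that it falls on the dosing date. If all three hold, the Visit 13 post-dose change is zero and the losses in the table above (1 of 4 vital-sign sets, 1 of 3 ECGs) apply to the subjects concerned. Later changes then move by an unknown d. If the Part A baseline is used, there is no effect.

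Only descriptive Part B vital-sign and ECG summaries are exposed. PANSS, weight, laboratory values, all Part A analyses, adverse events and listings are not. Severity is minor. Confidence is high in the wording defect, but the documents do not allow its impact to be sized.

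**What to change.** In SAP 3.1.1, replace the Part B sentence with: *The Part B baseline is the last non-missing observation before the first Part B dose at Visit 13, by date and time, or the planned pre-dose reading if no time is recorded. Visit 13 post-dose readings are post-baseline Part B values.* Leave the Part A definition as it is.

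In 3.7.4 and 3.7.5, add one sentence each naming the baseline used for Part B changes, for the Table 5 and Table 6 criteria, and for the post-baseline window of the orthostatic counts. This is worth doing even if the Part A baseline was always intended.

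The cost is two sentences in 3.1.1 and one in each of the other two sections. Pre-dose and post-dose readings are already collected, so no new data or procedures are needed.

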3.2 DEFINITIONS OF ANALYSIS SETS (POPULATIONS)

3.2.1 Enrolled Population

Enrolled population is defined as all subjects who enrolled in the study and received at least one dose of olanzapine before randomization.

3.2.2 Efficacy Populations

The efficacy analysis will be conducted on 2 analysis populations:

- FAS 1 Population is defined as all randomized subjects who received at least one dose of study drug and have at least one post-baseline assessment of PANSS total score.
- FAS 2 Population is defined as all FAS 1 subjects who gained weight during the first week of olanzapine treatment prior to randomization and have at least one post-baseline weight assessment.

FAS 1 population will be the primary efficacy population for analyses on all efficacy variables.

3.2.3 Safety Population

- Safety Population is defined as all randomized subjects who received at least 1 dose of study drug.
- Safety Population for Part B is defined as all randomized subjects who enrolled in Part B and received at least 1 dose of study drug in Part B.

3.3 DISPOSITION

The subject disposition will be summarized for the enrolled population by treatment group and overall and will include the following

- Subjects who were randomized
- Subjects in Safety Population
- Subjects in the FAS 1 Population
- Subjects in the FAS 2 Population
- Subjects who completed the olanzapine lead-in period and continued into Part A
- Subjects who discontinued the study during the olanzapine lead-in period along with reasons for discontinuation
- Subjects who completed the Part A placebo-controlled period and continued into Part B
- Subjects who discontinued the study during Part A placebo-controlled period along with reasons for discontinuation

- Subjects in Safety Population for Part B
- Subjects who completed Part B ALKS 3831 treatment period
- Subjects who discontinued the study during Part B ALKS 3831 treatment period along with reasons for discontinuation
- Subjects entering the safety follow-up period will include
 - Subjects who completed the safety follow-up after discontinuation in the olanzapine lead-in period
 - Subjects who discontinued the safety follow-up after discontinuation in the olanzapine lead-in period
 - Subjects who completed the safety follow-up after discontinuation in Part A placebo-controlled period
 - Subjects who discontinued during the safety follow-up period after discontinuation in Part A placebo-controlled period
 - Subjects who completed the safety follow-up after Part B ALKS 3831 treatment period
 - Subjects who discontinued during the safety follow-up period after Part B ALKS 3831 period

3.4 DEMOGRAPHICS AND BASELINE CHARACTERISTICS

Demographics and baseline characteristics such as gender, age, race, ethnicity, weight, BMI, PANSS, and CGI-S will be summarized by treatment group and overall for FAS 1 Population, FAS 2 Population, and Safety Population.

If there are heterogeneities between treatment groups in any of the subject characteristics that are of clinical importance or could affect the treatment outcome, the impact of the imbalances will be investigated and, if necessary, appropriate adjustments will be considered in the efficacy and safety analyses.

Medical and psychiatric history will be summarized by treatment group and overall using the number and percentage of subjects by category for the Safety Population.

